6.2.2 Observational period and Study Completion

Eligibility criteria that apply at Visit 2 must be re-checked before proceeding with Visit 2.

The observational period begins after the subject completes Visit 2 and ends after completion of Visit 7 at Week 156 or after the discontinuation visit. Procedures listed under each visit in the [flowchart](#) should be completed. Visit windows should be adhered as specified in the flowchart.

All visits during the observational period should be scheduled to start in the mornings according to Visit 1. Restriction check, smoking status, pregnancy test (if applicable) and IRT subject visit registration should be done first. Other checks include review of concomitant medication, MESI and AE. Physical examination and vital sign assessment (including pulse oximetry) will be performed additionally at Visits 5, 6, and 7.

The sequence of procedures will be the completion of the questionnaires mMRC, CAT and SGRQ, followed by ECG and pre PFT. Post PFTs should be done prior to post D_{LCO} /bodyplethysmography. Chest CT (and MRI, if applicable) should be performed between 1h and 4h after the end of the salbutamol (albuterol) administration (post-bronchodilator testing) at timepoints indicated in the [flowchart](#). 6 MWT should be performed after post PFT/ D_{LCO} /bodyplethysmography. Blood samples for safety and biomarker assessment should be collected after the ECG procedure is completed. Collection of induced sputum (if applicable) should be the last procedure. A spirometric device will be used to perform the PFTs and monitor subject's lung function during sputum induction. The BODE index will be calculated at visit 2, 6, and 7 in patients with COPD/COPD and A1ATD only.

If the scheduled visit does not occur within the protocol allowed time window, follow instructions provided in [Section 6.1.1](#) for rescheduling. Unscheduled visits may be arranged if necessary and the procedures completed during the unscheduled visit will depend on the circumstances under which the visit was scheduled.

Telephone contacts between clinic visits

Study sites will follow up subjects and collect information by telephone interviews at the dates indicated in the flowchart and will perform an IRT subject visit registration call. A subjects' reminder card will be provided to assist their memory recall in terms of respiratory symptoms, COPD exacerbations, hospitalization or interim health care visits, and concomitant therapy.

At each telephone contact, the investigator or delegate will review with the subject new occurrences of MESI (including COPD exacerbation: new occurrence of exacerbation, respiratory symptoms, COPD exacerbation-related hospitalization and other pertaining information) and will record it in the eCRF. If subjects are hospitalized, the study site might consider collecting and reviewing pertinent medical records (hospital records, telephone or written correspondence with primary physicians, discharge summaries, and death certificates) so that an informed judgment can be made as to the primary cause for admission.

In case of hospitalizations, subjects will be encouraged to promptly inform the study site prior to their regularly scheduled telephone interviews.

Details of all COPD exacerbations will be captured in the source notes.

Study Completion

Visit 7/ discontinuation visit will mark the end of the study period, and the subject has completed the study.

Discontinuation during the observational period

If a subject discontinues from the study during the observational period, the subject should be asked to come to the site for a discontinuation visit at the time of the next scheduled visit. The subject will undergo the procedures of this particular visit as outlined in the flowchart. If not possible, the subject should be encouraged to at least undergo the procedures for safety assessments. Women who become pregnant should undergo the procedures for safety assessments only.

Vital Status and COPD exacerbation status collection (Phone Call):

The objective of the phone call is to collect information on vital status (dead or alive) and COPD exacerbation status (COPD exacerbation status only in patients with COPD and patients with COPD and A1AT deficiency) in the time interval between the subjects' discontinuation date from the observational period and their hypothetical Visit 7 date. No other MESI will be collected during the phone call.

Depending on the point in time when the subject discontinues, the vital status and COPD exacerbation status collection phone call will be scheduled as follows:

Discontinuation date between Visit 2 and 5 will result in 3 telephone calls:

1. First collection: predicted 52 weeks ($D364 \pm 14$) from Visit 2
2. Second collection: predicted 104 weeks ($D728 \pm 14$) from Visit 2
3. Third collection: predicted 156 weeks ($D1092 \pm 14$) from Visit 2

Discontinuation date between Visit 5 and 6 will result in 2 telephone calls:

1. First collection: predicted 104 weeks ($D728 \pm 14$) from Visit 2
2. Second collection: predicted 156 weeks ($D1092 \pm 14$) from Visit 2

Discontinuation date between Visit 6 and 7 will result in 1 telephone call:

1. First collection: predicted 156 weeks ($D1092 \pm 14$) from Visit 2

If death occurs, the investigator will review the circumstances, including the relevant medical records to ascertain the most likely primary cause, if possible. Vital status and COPD exacerbation status information will be collected in accordance with national ethical and regulatory guidelines.

The purpose of the Vital Status and COPD exacerbation status collection will be explained to subjects prior to their participation in the study and will be part of the written informed consent.

Informed consent procedure and Vital Status and COPD exacerbation status information collection:

All subjects should be asked again at the timepoint of discontinuation, if they still agree to participate in the Vital Status and COPD exacerbation status collection part of the study. The decision must be documented in the subjects' charts.

7. STATISTICAL METHODS AND DETERMINATION OF SAMPLE SIZE

7.1 STATISTICAL DESIGN - MODEL

[REDACTED]

[REDACTED]

All subjects entering the study will be included in the analyses. Protocol violations will be defined in TSAP. Per-protocol set will be defined accordingly thereafter.

7.2 NULL AND ALTERNATIVE HYPOTHESES

No statistical hypotheses in a confirmatory sense are planned. All statistical tests are exploratory.

7.3 PLANNED ANALYSES

Variables to be analyzed are:

- Soluble biomarkers: assessments are made from blood sample (whole blood, serum, and plasma), and induced sputum. [REDACTED]. See [Section 5.8](#) for details.
- Imaging biomarkers: assessments are made from CT and MRI. [REDACTED] See [Sections 5.2](#) and [5.3](#) for details.
- Clinical and disease progression biomarkers: assessments are standard clinical measurements for patients with COPD. Examples are FEV₁, mMRC, or 6 MWT. See [Sections 5.4](#), [5.5](#), [5.6](#), [5.10](#), [5.11](#) and [5.12](#) for details.
- Medical events of special interest: they include pre-defined disorders and their intensities (additional other events might be reported at the discretion of the investigators). Examples are COPD exacerbations, heart failure or obesity. See [Section 5.7](#) for details.
- Safety assessments: They include, for example, laboratory parameters, adverse events and their intensities. See [Section 5.9](#) for details.

Subjects' demographics and medical history are summarized. They may be included in regression models to adjust for potential confounding.

7.3.1 Primary analyses

7.3.1.1 Descriptive and Summary Statistics

Continuous variables are characterized by their distributional summary statistics. Ordinal, counts, and categorical variables are summarized by counts and frequencies. Statistics are computed for each subject group (healthy subjects, GOLD 1, GOLD 2, GOLD 3, and COPD with A1ATD), and for all subjects combined when appropriate.

For variables measured for more than once during the course of the study, descriptive statistics are provided at each time point. In addition, if they are continuous, changes from baseline are calculated by subtracting baseline values from post-baseline values. Summary statistics are presented for each change by each subject group and by all subjects combined. Their 95% confidence intervals are also presented.

Summary plots such as histograms, barplots, or boxplots are produced as visual aids for understanding the distributions of these variables.

7.3.1.2 Correlations

Correlations between different biomarkers and between biomarkers and clinical assessments are estimated using Pearson or Spearman correlations for each subject group and for all subjects combined. Correlations between changes from baseline of the biomarker values are similarly estimated. Scatterplots are produced in addition.

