7.7 DETERMINATION OF SAMPLE SIZE

Due to the exploratory nature of the study, power computations are focused on attaining desired precisions for biomarker estimates and relevant clinical assessments in all COPD patient groups except for the A1ATD group.

Calculations are performed in SAS 9.3 using PROC POWER procedure. By assuming up to a 20% dropout rate, at least 100 subjects are expected to contribute to the analysis at the end of 3-year study period. The computations are thus based on 100 subjects in each COPD patient group.

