7.7.3 Power Computation based on Partial Pearson Correlation Coefficients

In addition, with 100 subjects in each group by allowing for up to 15 covariates, a partial Pearson correlation coefficient of 0.30 can be declared significant with 80% power between any two continuous variables (e.g. FEV₁ and a new biomarker) within the group.

[Table 7.7.3: 1](#) below provides additional details.

Table 7.7.3: 1 Power for a given Pearson correlation coefficient (alpha = 0.05, two-sided tests, n = 100)

Partial Pearson correlation	# of partial variables			
	0	5	10	15
0.25	0.715	0.692	0.668	0.643
0.30	0.865	0.847	0.827	0.805
0.35	0.951	0.941	0.929	0.914
0.40	0.987	0.983	0.978	0.971

The results from these calculations indicate the study has adequate power to estimate the biomarker values from the assessments described in previous sections.

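### Within-group correlations in Protocol 7.3.1.2 are unadjusted although 7.7.3 highlights partial correlations; the risk is confounding of absolute-unit measures, not lack of power

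*Protocol*

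**What the plan says.** Protocol 7.3.1.2 stands under 7.3.1 (Primary analyses): "Correlations between different biomarkers and between biomarkers and clinical assessments are estimated using Pearson or Spearman correlations for each subject group". The same method is used for all subjects together and for correlations of changes from baseline. No covariates and no partial correlation are mentioned.

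Protocol 7.7.3 states its power differently. Taking n = 100 per group and as many as 15 adjustment variables, it says that "a partial Pearson correlation coefficient of 0.30 can be declared significant with 80% power", and this is said to hold "between any two continuous variables (e.g. FEV₁ and a new biomarker) within the group". Table 7.7.3: 1 has columns for 0, 5, 10 and 15 partialled variables.

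Adjustment appears elsewhere in the plan. For demographics and medical history, Protocol 7.3 says: "They may be included in regression models to adjust for potential confounding". Section 7.3.1.3 adjusts the baseline comparisons between groups, and 7.3.1.4 adjusts regression models of change for baseline covariates that it does not list. Section 7.2 makes all tests exploratory.

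SAP 4.2 reports no change from the protocol's planned analyses. The SAP text available here describes no correlation method, but its sections 5.3, 7.6 and 9 are not visible.

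**The concern.** The correlation that the protocol highlights for power is adjusted, and the one it plans to report is not. The difference matters most for the example in 7.7.3, FEV1 against a new biomarker, inside a GOLD grade. Protocol 3.3.3.1 defines the grades by post-bronchodilator FEV1 % predicted: at least 80, 50 to below 80, and 30 to below 50. FEV1 in litres is % predicted times the predicted value. Holding the first factor in a band leaves much of the spread to the second, which is a function of age, sex and height. A biomarker that merely tracks those characteristics will then correlate with FEV1 in litres within a grade. The same reasoning applies to other measures in absolute units that scale with body size.

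The study is meant to find biomarkers that could support drug development (Protocol 2.1). A marker of sex or stature could be carried forward as a marker of disease.

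**Working it through.** **1. The protocol's own figure.** Inputs from 7.7 and 7.7.3: n = 100 per COPD group (125 × 0.8), two-sided alpha 0.05, rho = 0.30, p partialled variables. With Fisher's z, the mean is atanh(rho) + rho/(2(n − 1 − p)) and the standard error is 1/√(n − 3 − p).

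- p = 0: (0.3095 + 0.0015) × √97 = 3.063; power = Φ(3.063 − 1.960) = 0.865.
- p = 15: (0.3095 + 0.0018) × √82 = 2.819; power = Φ(0.859) = 0.805.

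All 16 cells of Table 7.7.3: 1 reproduce to three decimals. The raw correlation that 7.3.1.2 plans is the p = 0 column and has the higher power.

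**2. Share of FEV1 in litres due to the predicted value.** Assumptions, none from the documents:

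- % predicted is uniform on 80–110, 50–80 and 30–50 for GOLD 1, 2 and 3 (the protocol sets no ceiling for GOLD 1);
- it is independent of the predicted value;
- the predicted value has CV c = 0.20.

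Let k = variance of % predicted divided by its squared mean. Then R² = c² / (c² + k(1 + c²)).

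- GOLD 1: k = 75/95² = 0.00831; R² = 0.04/(0.04 + 0.00864) = 0.822; √R² = 0.907.
- GOLD 2: k = 75/65² = 0.01775; R² = 0.04/(0.04 + 0.01846) = 0.684; √R² = 0.827.
- GOLD 3: k = 33.3/40² = 0.02083; R² = 0.04/(0.04 + 0.02167) = 0.649; √R² = 0.805.

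For c from 0.15 to 0.25 the same formula gives R² between 0.51 and 0.88.

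**3. Raw correlation of a biomarker with no disease link.** If it correlates rho_B with predicted FEV1 (also assumed), the raw within-grade correlation is rho_B × √R². The smallest significant |r| at n = 100 is 0.197. The chance of significance comes from the formula in step 1 with p = 0.

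| rho_B | Raw r (GOLD 3 to GOLD 1) | Significant at 5% |
|---|---|---|
| 0.1 | 0.081 to 0.091 | 13% to 15% |
| 0.2 | 0.161 to 0.181 | 36% to 44% |
| 0.3 | 0.242 to 0.272 | 68% to 79% |

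Simulation gave 12–15%, 36–44% and 67–79%. Partialling out the predicted value brought the rate to about 5% in every case.

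**4. Check without the GOLD bands.** If covariates explain shares R²x and R²y of two variables through the same linear combination and the partial correlation is zero, the raw correlation is √(R²x × R²y), which is the maximum. Assumed shares of 5%/5%, 10%/10%, 20%/20% and 30%/30% give 0.05, 0.10, 0.20 and 0.30, significant at n = 100 in about 8%, 17%, 52% and 87% of cases. In simulation, the partial correlation on three covariates stayed at 4.6% to 5.2%.

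**The case against.** A reader might infer that the 80% power belongs to an analysis the study will not run, so that the correlations are underpowered. The documents do not support this. The zero-covariate column covers the raw Pearson correlation, and 7.7 says the sample size is mainly about precision, with correlation power as an addition.

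A reader might also infer that age, sex and body size alone will produce correlations near the 0.30 design value. No document gives their association with any biomarker or outcome. With rho_B = 0.1 the raw r stays below 0.10, and 0.30 in step 4 needs, for example, 30% of both variables explained in the same pattern.

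The other side has four further points:

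- In linear regression, the test of one biomarker given covariates is the partial-correlation test, so 7.3.1.4 supplies an adjusted primary analysis. This stands for models of change; it does not adjust the coefficients of 7.3.1.2.
- The main outcomes are change in lung density, FEV1 decline and exacerbations, whereas the mechanism concerns levels in absolute units. This stands: confounding of the progression correlations is not shown.
- The correlations are to be estimated and all tests are exploratory. This lowers the stakes but does not remove bias from a reported coefficient.
- SAP sections not visible here may specify covariates. They may, so no claim is made about the whole SAP.

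**Conclusion.** The concern holds in a limited form. As written, 7.3.1.2 gives unadjusted within-group coefficients, and the adjustments in 7.3, 7.3.1.3 and 7.3.1.4 do not reach them. For levels in absolute units, above all FEV1 in litres within a GOLD grade, these coefficients can carry confounding by age, sex and height. The size runs from minor to serious with the assumed link between biomarker and predicted FEV1: a false-positive rate near 12–15% at 0.1, but 67–79% at 0.3. It rests on uniform % predicted, a 20% CV of predicted FEV1, and an adjustment that captures the predicted value. There is no power deficit, and nothing is shown for changes from baseline or % predicted values. The point merits a wording change and does not challenge the design.

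**What to change.** In Protocol 7.3.1.2, and in the SAP's correlation section if it is silent, report beside each raw coefficient a partial Pearson or Spearman correlation adjusted for age, sex and height, within the ex-smoking control and GOLD 1–3 groups. Pack-years may be added. BMI belongs only in a sensitivity analysis, because it is a component of the BODE index (Protocol 10.6). Section 7.7.3 names no covariates, so the list must be stated. For absolute-unit measures, base any claim of biomarker association on the adjusted value. In the A1ATD group (up to 20 patients) keep raw coefficients only. If a SAP section not visible here already does this, a cross-reference is enough.

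The covariates are already collected, so the programming cost is slight. By Table 7.7.3: 1, power at r = 0.30 and n = 100 falls from 0.865 to 0.847 with 5 covariates; the formula in step 1 gives 0.855 with 3. The loss grows in smaller sets: with 3 covariates it is 0.654 to 0.631 at n = 60 (controls, before dropout) and 0.373 to 0.339 at n = 30 (an MRI stratum).

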Name of company:	Boehringer Ingelheim		
Name of finished product:			
n/a			
Name of active ingredient:			
n/a			
Protocol date: 02 Sep 2015	Study number: 352.2069		Revision date: 24 Feb 2020
Main criteria for inclusion:	
• COPD and healthy subjects of both sex aged ≥ 40 and ≤ 70 years• COPD with A1ATD of both sex aged ≥ 30 and ≤ 70 years• COPD and healthy ex-smokers with a smoking history ≥ 20 pack years• COPD with A1ATD ex-smokers with a smoking history ≥ 10 pack years• Body mass index (BMI) of ≥ 18 and ≤ 35 kg/m^2 (≤ 30 kg/m^2 in the MRI substudy)		
Duration of observation:	156 weeks (~ 3 years)		
Assessments:	
Clinical assessments:
 
• Spirometry• Body plethysmography• Pulse oximetry• Diffusing capacity of the lung for carbon monoxide• Questionnaires: mMRC, CAT, SGRQ• BODE index• 6 minute walk test (6 MWT)• Medical Events of Special Interest (MESI)• Adverse Events 
Biofluids:
 
• Blood• Induced Sputum (at selected sites) 
Imaging assessments:
 
• Chest CT (inspiratory/expiratory)• Magnetic Resonance Imaging (MRI) (in a subset of healthy subjects and patients with COPD without A1ATD)		
Biobanking:	Unspecified biomarker testing in blood in all subjects and sputum in a subset of subjects		
Safety criteria:	Vital signs, physical examination, safety laboratory, urine pregnancy testing, 12-lead electrocardiogram (ECG) and adverse event reporting		
Statistical methods:	Descriptive statistics, Pearson and rank-based correlation, multivariate statistical prediction model		

FLOWCHART

Study Periods	Screening Period	Observational Period									
		1	2	3	4	5	6	7	8	9	10
Visit		1									
Weeks			12	26	39	52	65	78	91	104	
Days	Prior to any study related procedure	-28 to -1	1	84	182	273	364	455	546	637	728
Time window for visits			see ¹⁷	± 7d	± 14d	± 14d	± 14d	± 14d	± 14d	± 14d	± 14d
Informed consent ¹	X										
Demographics	X										
Medical history	X										
Physical examination, BMI ¹⁰	X						X				X
Vital signs	X						X				X
Review of in-/exclusion criteria	X	X ¹²									
MESI Check	X	X	X	X	X	X	X	X	X	X	X
Smoking Status/Cotinine Test ¹⁸	X	X	X	X			X				X
Restrictions Check ⁸	X	X		X			X				X
Urine pregnancy test ²	X	X		X			X				X
Safety laboratory ^{3,5}	X	X	X	X			X				X
A1ATD testing ¹⁴	X										
12 lead-ECG	X						X				X
BODE index ¹⁵		X									X
mMRC ⁴	X	X					X				X
CAT ⁴		X					X				X
SGRQ ⁴		X					X				X

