3.3 SELECTION OF STUDY POPULATION

It is planned to enroll 60 healthy subjects, 125 patients with COPD of mild, 125 patients of moderate, 125 patients of severe disease stage and up to 20 patients with COPD and A1AT deficiency in approximately 50 sites.

A log of all subjects enrolled into the study (i.e. who have signed informed consent) will be maintained in the ISF at the investigational site irrespective of whether they have entered the observational period or not.

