3.3.3 Patients with COPD

3.3.3.1 Inclusion criteria

1. All patients must sign an informed consent consistent with ICH-GCP guidelines prior to participation in the study, which also includes the application of study restrictions.
2. Patients must be male or female outpatient.
3. Patients must be between the ages of ≥ 40 and ≤ 70 years.
4. Patients must have a body mass index (BMI) of ≥ 18 and ≤ 35 kg/m² (≤ 30 kg/m² in the MRI subset).
5. Patients must have a current diagnosis of COPD made by a physician prior to or during Visit 1 and an mMRC [[R00-0206](#)] score of 1 or more. The diagnosis of COPD must be in accordance with the GOLD Guidelines [[P15-01740](#)] and must be documented by the following criteria:

Known relatively stable airway obstruction with a post-bronchodilator FEV₁/FVC < 70 %.

6. The current COPD must be mild, moderate or severe based on lung function and symptoms and the clinical situation must have been stabilized for at least 4 weeks prior to Visit 1. The following definitions adapted from the GOLD Guidelines [[P15-01740](#)] apply:
 - a. Mild: post-bronchodilator FEV₁ $\geq 80\%$ of predicted normal (GLI 2012 [[R15-0845](#)] and JRS 2014 [[R15-2073](#)] at Visit 1).
 - b. Moderate: $50\% \leq$ post-bronchodilator FEV₁ < 80% of predicted normal (GLI 2012 [[R15-0845](#)] and JRS 2014 [[R15-2073](#)] without chronic respiratory failure at Visit 1).
 - c. Severe: $30\% \leq$ post-bronchodilator FEV₁ < 50% of predicted normal (GLI 2012 [[R15-0845](#)] and JRS 2014 [[R15-2073](#)] without chronic respiratory failure at Visit 1).
7. Patients must be ex-smokers for at least 9 months with a smoking history of ≥ 20 pack years (see [appendix 10.4](#), calculation of number of pack years).
8. Patients must be able to perform all study related procedures including technically acceptable pulmonary function tests, body plethysmography, D_{LCO}, sputum induction (if applicable), chest CT, and MRI (if applicable).
9. Patients must be on stable therapy (not limited to respiratory medication) for the last 4 weeks prior to Visit 1.

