4.2 CHANGES

There were no changes to the planned analyses as compared to what was described in the CSP. However, the structure of the planned analyses in the TSAP is not consistent to Section 7 of the CSP. This change was necessary to allow for a better understanding of order and importance of the conducted analyses.

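### Combined-group correlations carry no term for subject group, so severity differences between groups can read as association within them

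*Protocol*

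**What the plan says.** Protocol Section 7.3.1.2, under the primary analyses, states that correlations among biomarkers and between biomarkers and clinical assessments "are estimated using Pearson or Spearman correlations for each subject group and for all subjects combined". It extends this to change scores: "Correlations between changes from baseline of the biomarker values are similarly estimated". The synopsis is equally plain: "Pearson and rank-based correlation, multivariate statistical prediction model". None of these places names a group term, a stratified estimate or a partial correlation. The neighbouring Sections 7.3.1.3 (baseline comparisons) and 7.3.1.4 (predictive models) do state covariate adjustment.

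The groups are quotas: "It is planned to enroll 60 healthy subjects, 125 patients with COPD of mild, 125 patients of moderate, 125 patients of severe disease stage", plus up to 20 patients with A1AT deficiency. Section 3.1.1 closes recruitment group by group. The COPD groups are formed by severity ("The current COPD must be mild, moderate or severe based on lung function and symptoms", Section 3.3.3.1), using bands of FEV1 percent predicted.

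SAP Section 4.2 states: "There were no changes to the planned analyses as compared to what was described in the CSP". SAP Sections 4.1 and 6.1 present results by diagnosis group and for GOLD 1, 2 and 3 combined. The visible SAP neither repeats nor withdraws the pooling of all subjects, and it gives no rule for correlations.

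Partial correlation appears only in Protocol Section 7.7.3, where "a partial Pearson correlation coefficient of 0.30 can be declared significant with 80% power". That statement concerns correlations within one group.

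**The concern.** The study's overall objective is to explore whether biomarkers correlate with disease progression. When groups are sampled at deliberately different severity, any two measures that both vary with severity will correlate in the pooled data, even if they are unrelated among patients of the same grade. The size of that coefficient depends partly on the quotas: other group sizes would give another value with no change in biology. The reverse can also happen. If group means move in opposite directions, pooling can hide a real association within groups.

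The combined figure rests on more subjects than any by-group figure, and the visible documents do not say which leads or how a disagreement is to be read. At stake is how a biomarker's link to progression is described, in a study meant to identify useful biomarkers.

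**Working it through.** **The plan's own figure.** The only correlation calculation in the documents is Protocol Table 7.7.3: 1. For r = 0.30, n = 100, 15 covariates and two-sided alpha 0.05, Fisher z with its bias term gives [atanh(0.30) + 0.30/(2 × 84)] × √82 = (0.3095 + 0.0018) × 9.055 = 2.819. Power is Φ(2.819 − 1.960) = 0.805, as tabulated. All 16 cells reproduce. The same table gives 0.865 for r = 0.30 with no covariates.

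**Inputs.** Protocol Section 7.7 plans on 100 evaluable per COPD group: "By assuming up to a 20% dropout rate, at least 100 subjects are expected to contribute to the analysis" (125 × 0.8 = 100). Applying the same 80% to the other two groups is an assumption; it gives 48 controls and 16 A1ATD, so N = 48 + 300 + 16 = 364. Equal retention leaves the pooled r unchanged. The documents give no between-group differences, so the shift d (in within-group SDs per step from controls through GOLD 3) is an assumption and is varied.

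**Formula.** With unit within-group variance and within-group correlation ρ,

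pooled r = (ρ + B12) / √[(1 + B11)(1 + B22)],

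where B is the size-weighted between-group (co)variance. If both measures shift by d and ρ = 0, this is B/(1 + B).

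- GOLD 1-3, 100 each, at 0, d, 2d: B = (2/3)d².
- Five groups, A1ATD placed with GOLD 3: mean position (100 + 200 + 348)/364 = 1.780; mean square (100 + 400 + 1044)/364 = 4.242; B = (4.242 − 3.169)d² = 1.073d².

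| d | GOLD 1-3: B | GOLD 1-3: r | Five groups: B | Five groups: r |
|---|---|---|---|---|
| 0.25 | 0.042 | 0.04 | 0.067 | 0.06 |
| 0.5 | 0.167 | 0.14 | 0.268 | 0.21 |
| 0.75 | 0.375 | 0.27 | 0.603 | 0.38 |
| 1.0 | 0.667 | 0.40 | 1.073 | 0.52 |

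Placing A1ATD at the GOLD 2 level instead gives 0.06, 0.20, 0.36 and 0.50, so that choice matters little.

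**Simulation check** (2,000 data sets per setting, within-group correlation zero). For GOLD 1-3 at n = 300 the mean raw coefficients match the table. The raw Pearson test has p < 0.05 in 11%, 71%, 99.9% and 100% of runs for the four values of d. With group partialled out, the mean correlation is 0.00 and the rejection rate 5 to 6%. Spearman behaves almost the same as Pearson (0.04, 0.14, 0.28, 0.41).

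**Shift that yields r = 0.30 from nothing.** For GOLD 1-3, (2/3)d² = 0.30/0.70, so d = 0.80.

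**A level that defines the groups.** If one measure shifts 2 SD per grade, as FEV1 level might, and the other 0.5 SD, GOLD 1-3 gives (2/3 × 2 × 0.5)/√[(1 + 2.667)(1 + 0.167)] = 0.667/2.068 = 0.32.

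**Change scores.** If a biomarker shifts 1 SD per grade but the change score only 0.1 SD, GOLD 1-3 gives 0.067/√(1.667 × 1.007) = 0.05. The artefact is then negligible.

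**Masking.** With true within-group r = 0.30 and opposite shifts of 0.5 SD per grade, GOLD 1-3 gives (0.30 − 0.167)/1.167 = 0.11 and the five groups give (0.30 − 0.268)/1.268 = 0.03.

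**The case against.** Much of the opposing case stands.

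- **Safeguards are planned.** Section 7.3.1.2 also provides by-group correlations and scatterplots. Sections 7.3.1.4 and 7.3.2 plan regression and prediction models that use baseline covariates. A reader can compare the combined value with these.
- **The study is exploratory.** Section 7.2 plans no confirmatory hypothesis, so no error rate is being claimed and then broken.
- **The raw coefficient has a meaning.** It describes association across the sampled severity range. A reader might infer that it is invalid; the documents do not support that. Its limit is that it does not describe association among patients of similar severity.
- **The five-group figures are not the natural headline.** The visible SAP names GOLD 1-3 combined, where the artefact is smaller though not absent.
- **Progression is less exposed than level.** A reader might infer that biomarkers unrelated to progression will be promoted. That needs change itself to differ by grade, and Protocol Section 1.1 describes FEV1 decline as varying between patients whatever their starting grade. Nothing visible selects biomarkers on the combined coefficient, and pooling can weaken a correlation as well as strengthen it.
- **Section 7.7.3 is not a contradiction.** A reader might take its partial correlations as a promise that the combined analysis would be adjusted. It concerns one group of 100 and includes a column with no covariates.
- **Some SAP text is not shown.** The numbering passes from 7.5.2 to 7.7, Sections 5.3.x are cited but not visible, and the history table says that multivariate and descriptive analyses were defined in more detail. An adjustment may exist there.

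What remains is the protocol rule as written: a combined coefficient with no group term and no statement of how to read it when it disagrees with the by-group values.

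**Conclusion.** The point holds as an interpretation risk confined to the combined coefficients. With no association inside any group, the raw GOLD 1-3 correlation runs from 0.04 to 0.40, and the all-subjects correlation from about 0.06 to 0.52, as the assumed shift in both measures goes from 0.25 to 1.0 SD per grade. At 0.25 SD it is small; from 0.5 SD it is material for cross-sectional levels. These sizes rest on equal steps, a common within-group SD and shifts that the documents do not supply. They should not be read as a forecast for any particular biomarker, nor as a fault in the by-group correlations.

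**What to change.** For every combined analysis, whether all subjects or GOLD 1-3, report beside the raw coefficient a partial correlation given subject group (rank-based where Spearman is used) or a pooled within-group estimate. State that any claim that a biomarker relates to progression rests on the group-adjusted and by-group values. Label the raw coefficient as describing association across the sampled severity range. State also which poolings are intended, since the protocol names all subjects and the visible SAP names GOLD 1-3.

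The cost is a small change to the correlation code, a little more output and generally smaller combined coefficients. Because the COPD groups are FEV1 bands, adjusting for group also leaves less FEV1 variation when correlating with FEV1 level, which is a reason to keep both figures. No new data are needed. If SAP text not shown already adjusts for group, the sponsor need only confirm it.
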